Power calculations. Power calculations are difficult given the paucity of data about changes in the airway microbiome. This is explicitly an exploratory protocol to ascertain whether, in the short term, treatment of azithromycin in a small cohort of asthmatics changes the lower airway microbiome. We can generate potential power calculations based on the difference in (for example) relative abundance of pathogens in lower airway samples. For this protocol, a key goal is to obtain a good estimate of just how much the microbiome changes in response to azithromycin: if substantial, this trial will aid greatly our ability to make power calculations for larger trials. If changes are small, we will have a clear answer at a modest cost. For example, based on our preliminary published data (25), *Pseudomonas* abundance among asthma patients using ICS was $10.4 \pm 1.8\%$. Assuming 20 evaluable patients on azithromycin in a before and after analysis, we will have 80% power (two-sided $\alpha=0.05$) to detect a change in abundance of $\Delta=0.9$ to $\Delta=1.2$ if the within-patient correlation between pre- and post-treatment abundance is $\rho=0.7$ or $\rho=0.5$. The half-width of the 95% confidence interval for the change in abundance will be 0.7 to 0.84 if $\rho=0.7$ or $\rho=0.5$.

BIBLIOGRAPHY AND REFERENCES CITED

1. (EPR3) EPR. Guidelines for the Diagnosis and Management of Asthma. Bethesda: National Heart Lung and Blood Institute; 2007.
4. Braman SS. The global burden of asthma. *Chest.* 2006; 130(1 Suppl):4S-12S.

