This pilot protocol examines the change in the airway microbiome after azithromycin over an 8 week period. 40 subjects with poorly controlled asthma and 10 control subjects with no known lung disease will undergo clinical data collection including ACT score, lung function, exhaled nitric oxide (FeNO), methacholine challenge, and induced sputum and blood collection. Participants with asthma then are randomized 1:1 to receive azithromycin, 250 mg, or placebo, daily for 8 weeks. Clinical parameters including ACT, oral wash, adherence, side-effect profile, spirometry, and biological specimens (sputum, blood, FeNO) are collected again at 4 and 8 weeks. Control subjects undergo the same measurements, but do not receive any intervention.

Schedule of Events

	Asthma (A) or Control (C)	Visit 1/Week 0 (Screening) (+/- 3 days)	Visit 2/Week 4 (+/- 3 days)	Week 6 (+/- 3 days)	Visit 3/Week 8 (+/- 3 days)	Week 10 (+/- 3 days)	Visit 4/Week 12 (+/- 3 days)	Week 14 (+/- 3 days)
Informed Consent	A,C	X						
Site Visit	A,C	X	X		X		X	
Phone Call	A			X		X		X
Confirmation of Eligibility	A,C	X	X					
Randomization	A		X					
Drug Dispensation	A	X ^{1,2}	X ^{1,2,3}		X ^{1,2,3}		X ^{1,2}	
Demographics	A,C	X						
Medical History Review	A,C	X						
Asthma History	A	X						
Smoking History	A,C	X						
Concomitant Medication Review	A,C	X	X		X		X	
Physical Exam/Vital Signs	A,C	X	X		X		X	
Asthma Control Test	A	X						
Demographics Questionnaire	A,C	X						
Family History Questionnaire	A,C	X						
Work Exposures Questionnaire	A,C	X						
Home Exposures Questionnaire	A,C	X						
Physical Activity Questionnaire	A,C	X						
Secondhand Smoke Exposure Questionnaire	A,C	X						
Peak Flow Meter Readings ⁵	A	X	X	X	X	X	X	X
Electronic Diary ⁴	A	X	X	X	X	X	X	X
ECG	A,C	X	X		X		X	
Spirometry with Reversibility ⁶	A,C	X	X		X		X	
Exhaled NO	A,C	X	X		X		X	
Urine Pregnancy Test ⁷	A,C	X						
Methacholine Challenge ⁸	A,C	X	X		X		X	
Sputum Induction	A,C	X	X		X		X	
Oral Wash	A,C	X	X		X		X	
Complete Blood Count with Platelet Count and Differential Blood Sample	A,C	X			X			
Serum IgE Blood Sample	A,C	X						
RAST Blood Analysis	A,C	X						
Research Blood Samples	A,C	X			X			
Adverse Events Review	A,C		X	X	X	X	X	X
Compliance/Adherence to Diary and Study Drugs	A	X	X	X	X	X	X	X

1. Dispensation of albuterol to asthmatic subjects (if required at Visit 2 and Visit 3)
2. Dispensation of ICS/LABA to asthmatic subjects
3. Dispensation of azithromycin/placebo to asthmatic subjects

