4. Diary is completed twice daily by asthmatic subjects at home. Compliance will be reviewed at every visit (clinic or telephone).
5. Peak flow meter readings are done twice daily. Compliance will be reviewed at every visit (clinic or telephone).
6. Reversibility only conducted on those subjects with an $FEV1\% < 60\%$ predicted.
7. Only required for females of child-bearing potential
8. Methacholine challenge only conducted on subjects whose $FEV1\% > 60\%$ predicted.

Inclusion criteria (All participants):

1. Age 18 - 55 years
2. Able to provide informed consent
3. QTc < 440 ms on ECG
4. Smoking history < 10 pack-years

For subjects with poorly controlled asthma

1. Methacholine PC20 ≤ 16 mg/ml
2. Albuterol response $\geq 12\%$ on FEV1 after 4 puffs of albuterol
3. Ability to use combination ICS + LABA
4. Meet definition for Th2-low asthma: peripheral blood eosinophil count < 300 and exhaled nitric oxide level < 30 ppb.

Exclusion criteria:

1. History of allergy or intolerance to any medications used in this study
2. Medication exclusions:
 - a. Current use of medications that prolong QTc interval
 - b. Current use of omalizumab or other anti-IgE therapies
 - c. Current use of anti IL 5 therapies
 - d. Current use of anticoagulants
 - e. Prednisone or other oral steroids within past 3 months
3. Pregnancy or lactation
4. Other respiratory or inflammatory disorders (e.g., sarcoidosis, emphysema)
5. Pre-existing liver disease (AST or ALT $> 10\%$ above the upper limit of normal)
6. Smoking within the last 6 months
7. Exacerbation of asthma in past 3 months
8. Affected by a hearing disorder
9. Clinically significant medical condition (e.g., heart failure, seizure disorder) which may increase risk as determined by study investigator
10. Corrected QT interval > 450 msec. Patients with known cardiac history or prolonged QT interval on a screening EKG are excluded given the small but real potential for macrolide-related side effects (49-54).

Recruitment

Subjects will be recruited from the Pulmonary and General Medicine clinics at the University of Chicago and at Northwestern University. We will also use advertisements including online, flyer and posters.

Duration of protocol

Participation may be up to 14 weeks.

Location where research is to be conducted

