For subjects recruited at the University of Chicago, research is conducted in the Clinical Research Center (CRC) on W5 of the Gilman-Smith building. Some methods (e.g., methacholine) may be done in the Pulmonary Function Lab on the 5th floor of the DCAM building. For subjects recruited at Northwestern University, research is conducted at the Clinical Research Unit on the 11th floor of the Galter Pavilion. Samples and data collected at Northwestern will be sent to the University of Chicago.

Explanation of Tests and Procedures

1. Physical examination: Includes vital signs and examination of the cardiorespiratory system.
2. Asthma control test (ACT). This is a series of six questions (appended) that allow a patient to provide a numeric rating to key asthma symptoms. This is a research- and clinically-validated tool (61,62) and is a standard in the asthma research community.
3. Questionnaires. Subjects will be asked to complete six questionnaires. These questionnaires address subjects' home exposures, work exposures, family history, etc. These questionnaires should be completed by subjects at the visit 1.
4. Spirometry. The patient will be instructed at the time their visit is scheduled to hold beta agonist therapy and avoid caffeinated beverages for 12 hours prior to their study visit. If the subject's baseline FEV1 is below 60% of predicted value, the subject will receive 4 puffs of albuterol delivered by a metered dose inhaler. Spirometry will be repeated after 15 minutes in order to assess reversibility of obstruction.
5. Exhaled nitric oxide measurement. Subjects inhale deeply and then exhale slowly through the mouth into a tube. The exhaled gas is sampled and eNO measured.

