6. Methacholine aerosol challenge test. Subjects whose baseline FEV1>60% will inhale increasing concentrations of methacholine starting with saline diluent followed by: 0.025 mg/ml, 0.1 mg/ml, 0.25 mg/ml, 1.0 mg/ml, 2.5 mg/ml, 10 mg/ml and 25 mg/ml. Spirometry will be performed after each dose until a $\geq 20\%$ fall in the forced expiratory volume in one second is achieved or the highest dose of methacholine is administered. No further doses of methacholine will be administered once this threshold has been reached. The patient will then receive two puffs of albuterol via a metered dose inhaler and spirometry reassessed to ensure that the FEV1 has returned to within 10% of baseline. Participants will not be allowed to leave the center unless their FEV1 is within 10% of that visit's baseline.
7. Venipuncture to obtain 85ml of blood for safety and research samples.
 - a. RAST: The test is used to check for allergic sensitivity to specific substances. In the test, the sample of blood is mixed with substances known to trigger allergies. The test measures the level of allergy antibodies (specific IgE antibodies) in the blood which are present if there is an allergic reaction.
8. Electrocardiogram (ECG). This is done to obtain a corrected QT interval (QTc). If the QTc is longer than 450 ms, patients will not be eligible for study given the very small but real risk of azithromycin-related cardiac events (54,55).

9. Sputum induction. The subject will be asked to breathe in a salty mist for up to 12 minutes. Every two minutes the subject will be asked to cough deeply and strongly in order to bring up mucus. Subjects may clear their saliva at any time during the procedure. If the subject produces an adequate specimen in the first four minutes the procedure may be terminated early. Subjects are advised that their active participation is important and that they should provide us with a vigorous, deep cough to produce sputum. Sputum samples will be sent to either University of Chicago or Northwestern for cell counts.
10. Oral wash. Subjects will be asked to rinse saline around in their mouth and spit it into a cup.

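### The Schedule of Events omits the repeat ACT scores that the primary outcome needs, and asthma inclusion items 1 and 2 cannot both be tested at one visit

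*Combined protocol and SAP*

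**What the plan says.** **ACT.** Outcome Measures names the ACT change from week 0, labelled baseline, to 8 weeks as primary. Statistical analysis compares the arms by a two-sample t-test on each subject's own change. The Study Design text has ACT measured before treatment and again at 4 and 8 weeks. It includes the 10 controls in the initial collection and says that they have the same measurements as the asthma subjects. The ACT row of the Schedule of Events has a single mark, at Visit 1/Week 0, and is labelled for asthma subjects only.

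**Timeline.** Randomization is at Visit 2 (Week 4), after a four-week run-in. Study drug runs to Visit 4 (Week 12). The combination inhaler supplied by the trial starts on the day of Visit 1 and may differ from what the subject was taking (Asthma medications during the study).

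**Entry tests.** Under the asthma inclusion criteria, item 1 is "Methacholine PC20 ≤ 16 mg/ml". Item 2 is a response of at least 12% "on FEV1 after 4 puffs of albuterol". They are separate numbered items, in one list with items 3 and 4, and nothing joins them as alternatives. Footnote 6 to the schedule says "Reversibility only conducted on those subjects with an" FEV1 below 60% predicted, and footnote 8 says "Methacholine challenge only conducted on subjects whose" FEV1 is above 60%. The test descriptions repeat both limits: in item 4, if "baseline FEV1 is below 60% of predicted value, the subject will receive 4 puffs of albuterol"; in item 6, "Subjects whose baseline FEV1>60% will inhale increasing concentrations of methacholine".

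**The concern.** The table and the text disagree on whether the primary outcome is collected after Visit 1. A site that works from the table would obtain one ACT score per asthma subject and no change score. Even with the table corrected, a count of 0 to 8 weeks could run from Visit 1 or from randomization at Visit 2, and the two choices measure different things.

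On entry, the list as worded asks for two test results that the plan's own FEV1 limits keep apart. Staff at the two sites would have to decide for themselves how the items combine, and what to do at an FEV1 of exactly 60%.

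**Working it through.** **Inputs.** Visits 1, 2, 3 and 4 are at Weeks 0, 4, 8 and 12, and ACT is marked at Visit 1 only (Schedule of Events). Study drug runs from Visit 2 to Visit 4 (Study Drug). There are 40 asthma and 10 control subjects (Study Design). The plan has no power or precision figure for ACT. Its only power statement concerns *Pseudomonas* abundance and is not at issue here.

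**Step 1: can the ACT change be computed from the table?** It needs both scores.

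| Reading of baseline and 8 weeks | Visits | ACT marked | Weeks apart | Weeks on study drug |
|---|---|---|---|---|
| Schedule weeks | 1 and 3 | 1 of 2 | 8 − 0 = 8 | 8 − 4 = 4 |
| Treatment weeks | 2 and 4 | 0 of 2 | 12 − 4 = 8 | 12 − 4 = 8 |
| Mixed | 1 and 4 | 1 of 2 | 12 − 0 = 12 | 12 − 4 = 8 |

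No reading reaches 2 of 2, so from the table alone the change is available for 0 of 40 asthma subjects.

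**Step 2: which pair fits the stated outcome?** Only Visits 2 and 4 are eight weeks apart and cover the whole of study drug. Visits 1 and 3 combine the run-in, when the controller may change, with half of the treatment period. Randomization balances the run-in change between arms in expectation, so the arm difference would not be biased by it. That difference would, however, estimate a four-week effect, and the run-in change would be part of every subject's score.

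**Step 3: number of ACT assessments.**
- Table, asthma subjects: 40 × 1 = 40.
- Study Design text, asthma subjects: 40 × 3 = 120, a gap of 120 − 40 = 80.
- Study Design text as worded, with controls: (40 + 10) × 3 = 150, a gap of 150 − 40 = 110.

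**Step 4: the FEV1 limits at one visit.**

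| FEV1, % predicted | Reversibility test (item 2) | Methacholine (item 1) |
|---|---|---|
| Below 60 | done | not done |
| Exactly 60 | not done | not done |
| Above 60 | not done | done |

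No row gives both. Two other mentions of albuterol do not fill the gap. The two puffs after methacholine check recovery, and the nebulizer treatment mentioned under sputum-induction risks is not the four-puff test of item 2. The documents give no FEV1 distribution, so the number of subjects affected cannot be estimated.

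**The case against.** **On ACT.** The Study Design text, the primary outcome and its analysis all agree that ACT is repeated, and only one table row does not. A reader might infer that ACT is never repeated and the primary outcome will go unmeasured. The documents do not support that: the text plans the repeats, and 0 of 40 holds only if sites follow the table against it. What stands is the conflict itself, and the fact that no section names the two visits. Marks lost in reading the PDF are an unlikely explanation, since neighbouring rows with several visits kept theirs.

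**On items 1 and 2.** The two FEV1 limits are complementary, so an either/or is the evident intent, and a reading that admits nobody on one visit's testing is unlikely to be used. A reader might infer that no asthma subject can ever be eligible. That goes too far. "Confirmation of Eligibility" is marked at Visits 1 and 2, and a subject whose FEV1 crosses 60% between them could have both tests. The items also do not say that the qualifying result must come from a study visit. Nor does "unless their FEV1 is within 10% of that visit's baseline" settle how the 60% limit is applied, because that phrase belongs to the rule for leaving the center after methacholine. What stands is that the alternative is not written and that exactly 60% is assigned no test.

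**On poor control.** None of the four asthma items measures control, so a reader might infer that the target population is missing from the plan. It is not: the heading of those items and the Study Design text both state it. The term is undefined, which is a secondary clarification and not part of this finding.

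**Conclusion.** This is an internal inconsistency, wrong as written in two places.

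- **ACT.** The table supplies one ACT per asthma subject where the text supplies three (40 against 120 in total, or 150 if the controls are counted). From the table alone the primary change cannot be computed for anyone. The baseline and 8-week visits are undefined, and the choice decides whether the outcome reflects four or eight weeks of study drug. Whether controls complete ACT is also unresolved.
- **Entry tests.** On one visit's study testing, no FEV1 value allows both item 1 and item 2 to be met, and exactly 60% is a small further gap.

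The first part assumes that the table is complete as printed. The second is limited to tests done under the study's own FEV1 limits at a single visit. Neither part shows that the trial team intended anything other than repeat ACT and an either/or entry rule.

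**What to change.** **ACT.** Mark ACT at Visits 2, 3 and 4 in the Schedule of Events, in line with the Study Design text. In Outcome Measures and Statistical analysis, define baseline as the randomization visit (Visit 2) and 8 weeks as the end of study drug (Visit 4) for the primary outcome. State whether controls complete ACT, and make the table and text agree. The cost is table marks and a sentence or two. If the Visit 1 mark also stays, each asthma subject completes four ACTs (40 × 4 = 160). That is 40 more than the text implies, for a six-question form at visits already planned.

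**Entry tests.** Reconcile inclusion items 1 and 2 with footnotes 6 and 8 and with test descriptions 4 and 6. State how the two items combine and how an FEV1 of exactly 60% is handled. This is wording only, and no position is taken on which clinical rule is right.

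**Secondary clarification.** The sponsor may wish to write down what it means by poorly controlled asthma. That could narrow eligibility, and the correction above does not depend on it.

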The use of azithromycin is contraindicated in patients with known hypersensitivity to any macrolide or ketolide, or in patients with a history of cholestatic jaundice or hepatic dysfunction associated with prior use of azithromycin.

Common:

- Mild Diarrhea
- Nausea
- Abdominal pain
- Vomiting
- Mild rash
- Nervous feeling

-Sleep problems

Very Uncommon:

- Diarrhea that is watery or bloody
- Headache with chest pain and severe dizziness
- Ototoxicity (hearing loss)
- Fainting
- Fast or pounding heartbeats
- Nausea
- Upper stomach pain
- Itching
- Loss of appetite
- Dark urine
- Clay-colored stool
- Jaundice (yellowing of the skin or eyes); or
- Severe skin reaction -- fever, sore throat, swelling in face or tongue, burning in eyes, skin pain, followed by a red or purple skin rash that spreads (especially in the face or upper body) and causes blistering and peeling

Rare:

Azithromycin is an antibiotic. Like with any other antibiotic, bacteria in the body may develop resistance to the medicine over time. Because of this the body may not fight off these bacteria as well as it should fight them off if these bacteria were to cause an infection. While the practical risk of this is very low, given what we know about azithromycin and resistant bacteria, if the subject were to develop an infection during or immediately after this study such as a bronchitis (infection of the breathing tubes), ear infection, throat infection, or sinus infection, the doctors should treat them with an antibiotic other than azithromycin.

There are known drug interactions with neflifinavir and with warfarin. Previous asthma-related studies using azithromycin have demonstrated few severe adverse events (20,41,44,57,58).

Spirometry:

The spirometry test may cause some study subjects to feel short of breath, lightheaded or dizzy. Treatment will be available if this occurs.

Methacholine challenge testing:

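### Exclusion 1 is narrower than the protocol's own azithromycin contraindication: known hypersensitivity to another macrolide or a ketolide meets no mandatory exclusion

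*Combined protocol and SAP*

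**What the plan says.** In the combined protocol and SAP, item 1 of the Exclusion criteria reads "History of allergy or intolerance to any medications used in this study".

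The Azithromycin part of the Risks section gives two contraindications. The first concerns the drug class: "The use of azithromycin is contraindicated in patients with known hypersensitivity to any macrolide or ketolide". The second concerns the liver: "or in patients with a history of cholestatic jaundice or hepatic dysfunction associated with prior use of azithromycin".

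Two other exclusions come near the subject. Item 5 covers "Pre-existing liver disease", defined by AST or ALT. Item 9 covers a clinically significant medical condition "which may increase risk as determined by study investigator", with heart failure and seizure disorder as its examples.

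In the Schedule of Events, "Medical History Review" falls at Visit 1 and "Confirmation of Eligibility" at Visits 1 and 2; randomization is at Visit 2. Exposure is set out under Study Design: "Participants with asthma then are randomized 1:1 to receive azithromycin, 250 mg, or placebo, daily for 8 weeks". Controls receive no intervention.

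**The concern.** The contraindication covers a drug class, whereas the exclusion covers only the particular drugs given in the trial. A patient can fall inside the first and outside the second: someone with a known reaction to clarithromycin, for example, who has never taken azithromycin or has taken it without trouble.

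Eligibility is confirmed against the numbered criteria, and a hazard described only under Risks is not one of them. What is at stake is participant safety. A contraindicated patient could be given blinded azithromycin daily for 8 weeks, and the Risks section lists a severe skin reaction with facial or tongue swelling among the very uncommon effects of the drug. Nothing statistical depends on this point.

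**Working it through.** The plan states no figure on this point to reproduce. The check is a comparison of texts, followed by a short count of possible exposure.

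**Step 1: which medications does exclusion 1 reach?** The documents name these:
- azithromycin (Study Drug);
- fluticasone with salmeterol (Controller therapy);
- albuterol (Rescue therapy);
- methacholine, as the challenge agent (Explanation of Tests and Procedures, item 6).

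One is a macrolide, azithromycin. None is a ketolide. Exclusion 1 therefore reaches a past reaction to azithromycin and, as worded, no other member of either class.

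**Step 2: does any other criterion close the gap?**

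| Exclusion | Subject | Covers hypersensitivity to another macrolide or a ketolide? |
|---|---|---|
| 1 | Allergy or intolerance to trial medications | No |
| 2 | Concomitant medications | No |
| 3 | Pregnancy or lactation | No |
| 4 | Other respiratory or inflammatory disorders | No |
| 5 | Liver disease, by AST or ALT | No |
| 6 | Recent smoking | No |
| 7 | Recent asthma exacerbation | No |
| 8 | Hearing disorder | No |
| 9 | Medical condition judged by the investigator to raise risk | Only at discretion |
| 10 | QTc and cardiac history | No; it mentions macrolide side effects only in that context |

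Exclusions naming the class hypersensitivity: 0 of 10. The inclusion criteria do not address it either.

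**Step 3: the hepatic contraindication.** Liver injury attributed to earlier azithromycin is naturally read as intolerance to a trial medication, so exclusion 1 probably covers it without naming it. Exclusion 5 would not reliably catch it, because a past episode may have resolved and left normal AST and ALT. Of the 2 stated contraindications, then, 1 is plausibly covered and 1 is not.

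**Step 4: possible exposure.**
- Asthma subjects randomized: 40, in a 1:1 ratio, so 40 / 2 = 20 on azithromycin.
- If one contraindicated patient were randomized, the chance of azithromycin would be 20 / 40 = 0.5.
- Planned course: 7 × 8 = 56 daily doses.

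These figures describe exposure given that such a patient is randomized. They do not measure harm: the documents give neither the prevalence of class hypersensitivity nor a rate of cross-reaction.

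**The case against.** The strongest reply is that the protocol already contains the rule. The contraindication is current protocol text, nothing in the exclusion list permits treating a contraindicated patient, and an investigator who follows the whole document has a clear direction. Medical history is taken at Visit 1, eligibility is confirmed again at the randomization visit, and item 9 gives the investigator the means to exclude. A class-allergy question may also appear on the screening form, in the consent pages or in the Data Safety and Monitoring Plan, none of which is in the text available here. On this view the matter is only where a sentence is placed, and its practical consequence cannot be shown.

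Much of this stands. The safeguards are real, most clinicians would decline such a patient, and the gap does not show that the team overlooked the hazard. The exposure figures are conditional on an event whose probability is unknown.

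It does not remove the mismatch. The Risks statement is not one of the numbered criteria, and item 9 is discretionary and worded for medical conditions, which a past drug reaction does not obviously fit. Other azithromycin hazards were not left to judgement: QTc, QT-prolonging drugs, liver disease and hearing disorder each have their own exclusion. With two recruiting sites, a written criterion also makes uniform handling more likely. One could read allergy to a trial drug as extending to its class, but a safety criterion should not depend on a generous reading.

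**Conclusion.** The concern holds. As written, the eligibility list can admit an asthma patient whom the same protocol calls contraindicated for azithromycin. The gap is confined to known hypersensitivity to a macrolide other than azithromycin, or to a ketolide; the hepatic contraindication is probably covered already.

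The size in practice is probably very small and may be nil: some unknown number, possibly zero, among about 20 patients on azithromycin. The 10 controls are unaffected, and so is every estimate, power figure and conclusion.

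This rests on reading exclusion 1 literally and on the documents supplied. A class-allergy question on an unseen form would lower the practical risk but would not correct the criterion. The point is worth fixing because it concerns safety and the correction costs almost nothing.

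**What to change.** For asthma subjects, add to exclusion 1 a known hypersensitivity to any macrolide or ketolide. For completeness, also name past cholestatic jaundice or liver dysfunction linked to azithromycin. The eligibility list then agrees with the Risks section.

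The cost is one clause in the protocol and a matching line on any screening form. No visit or test is added, since eligibility is already confirmed at Visits 1 and 2. The downside is at most a rare extra screen failure, in a patient the protocol already regards as contraindicated.
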